9.8 Statistical Methods Planned in the Protocol and Determination of Sample Size

9.8.1 Statistical and Analytical Plan

Details for the statistical evaluation of the results will be given in a separate statistical analysis plan (SAP).

9.8.1.1 Software to be used

All statistical calculations will be carried out using SAS language and procedures (SAS 9.2 or higher version SAS-Institute, Cary NC, USA).

9.8.1.2 Eligibility for Statistical Evaluation

Eligibility of subjects will be determined within the data review meeting (DRM). The following patient populations will be investigated:

- Safety population: All subjects receiving at least once the study medication will be included into the safety evaluation (safety collective).
- Per protocol population: All subjects who have received both injections and who have not withdrawn within the first 7 days after the second injection will be included for the per protocol analysis.

All safety endpoints will be investigated in the safety population. As a sensitivity analyses, the analysis of the safety endpoints will be repeated in the per protocol population. All other endpoints will be investigated in the per protocol population only.

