8.4 Secondary Endpoints

- Humoral immunity: Magnitude of MERS-S-specific antibody responses as assayed by ELISA

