9.4 Treatments

9.4.1 Treatments Administered

All eligible subjects will be allocated to one of the two dose cohorts according to the assignment list. Each subject will receive two or three vaccine injections administered as i.m. injections in the deltoid region of the upper arm muscle.

For safety reasons dose administration in each dose level will be performed in four groups. Dose administration for the first subject at all dose levels will be vaccinated 48 hours prior to the second groups (second and third subject) of this dose level. The second and the third subject will be vaccinated in an interval of at least 5 min and after a period of at least 48 hours after the first subject to assess for immediate hypersensitivity reaction (within 60 min after the vaccination) or cytokine release (within 24 hours following the vaccination). The next group of four subjects can be vaccinated in parallel (in intervals of at least 5 min) at least 24 hours after the second group and at least 24 hours before the last group. The last group of the dose cohort including five subjects will be dosed on the same day in intervals of at least 5 min. Dosing events are supervised by an Investigator.

Figure 1: Dose administration groups

A Local Safety Board will be established for this study. Planned 2nd immunization and dose escalation will occur following a review of the interim safety report. Interim safety reports will contain safety data obtained until day 7.

The second immunization for each subject will be done after the Local Safety Board reviewed individual safety data of the respective subject.

All subjects who consented to the study extension will be immunized a third time with a vaccine dose of 1×10^8 pfu MVA-MERS-S at 12 months (± 4 months) after the first vaccination.

For the decision about dose escalation safety data obtained until day 7 after the second immunization of all subjects of the first cohort will be taken into account.

A dose level may be repeated and furthermore, additional dose step(s) may be added but not exceeding dose of 1×10^8 pfu MVA-MERS. The decision to repeat and/or to modify the dose level and/or to add additional dose steps will be taken by the Local Safety Board and the Ethics Committee and Competent Authority will be notified.

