9.4.10.3.4 Ambulatory Visits

Subjects will return to the study ward for ambulatory visits on study day 3, 7 and 14 (± 2), after the first vaccination and on study day 35, 42 (± 2), 56 (± 3), 84 (± 3) after the second vaccination. On the ambulatory visits the following events will be performed:

- Targeted Physical Examination (only on day 42)
- Vital signs/ Temperature
- 12-lead ECG (only on day 7, 14, 35, 42)
- Injection Site reaction & systemic events/ reaction assessment (only on day 3, 7, 14, 35 and 42)
- Safety Laboratory (Urine) (only on day 7, 14, 35, 42)
- Safety Laboratory (Blood) (only on day 3, 7, 14, 35, 42)
- Blood sampling for troponin (only on day 7, 14, 35, 42)
- Blood sampling for humoral immunogenicity (only on day 7, 14, 35, 42, 56, 84)
- Blood sampling for cellular response (only on day 14, 42, 56, 84)
- PBMC freezing and plasma aliquots
- Blood sampling for RNA storage (only on day 3, 7, 35)
- Blood sampling for innate immunity (only on day 3, 7, 35)
- Adverse events assessment
- Concomitant medication assessment
- Collection and review of diary

9.4.10.3.5 Ambulatory vaccination and subsequent ambulatory visits (only for subjects who gave consent to the study extension)

Subjects will return to the study ward for an ambulatory vaccination visit 12 months (± 4 months) after the first immunization.

The following interventions will be performed:

- Informed Consent
- I/E Criteria check
- Update medical history
- Weight
- Physical examination
- Vital signs / Temperature
- 12-lead ECG
- Injection Site reaction & systemic events/reaction assessment
- AE/ConMed
- Alcohol Breath Test
- Urine Drug Screen
- Urine Pregnancy Test
- Safety Laboratory (Urine/Blood)
- Blood sampling for humoral immunogenicity
- Blood sampling for cellular response
- PBMC freezing and plasma aliquots
- Blood sampling for RNA storage
- Blood sampling for troponin
- Blood sampling for innate immunity
- Dosing
- Training on subject diary

After dosing the following events will be performed **at 2 h, 4 h and 6 h**:

- Vital signs (and at 0 h, before dose administration)
- Temperature (and at 0 h, before dose administration)
- (AE)/ConMed (and at 0 h, before dose administration)
- Injection site reactions & systemic events/reactions assessment

Subjects will return to the study ward for ambulatory visits on study day 1, 3, 7 and 14 (± 2), after the third vaccination.

On the ambulatory visits the following events will be performed:

- Vital signs/ Temperature

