9.4.10.4 Early Termination

All enrolled subjects who complete the study, discontinue early, or withdraw from the study will have the follow-up assessments and procedures completed for their safety as outlined in Table 1. Subjects who discontinue early or withdraw from the study will be replaced if they discontinue early or withdraw up to day 35.

In some cases it may be necessary for subjects to return to CTC North for additional care, confinement, and/or follow-up. Circumstances in which this may be necessary are:

- Follow-up on abnormal laboratory evaluations
- Follow-up on an ongoing AE at the final visit
- All additional safety follow-up visits will be at the discretion of the investigator and the sponsor.

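### Antibody summaries at days 7, 14 and 28 are limited to subjects who later complete dose 2 plus 7 days; other vaccinated subjects' samples are listed but not summarised

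*Protocol*

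**What the plan says.** Protocol section 9.8.1.2 defines two populations. The safety population is every vaccinated subject: "All subjects receiving at least once the study medication will be included into the safety evaluation". The per protocol population is "All subjects who have received both injections and who have not withdrawn within the first 7 days after the second injection". Safety endpoints are analysed in the first and checked in the second: "As a sensitivity analyses, the analysis of the safety endpoints will be repeated in the per protocol population". For the rest, "All other endpoints will be investigated in the per protocol population only".

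The secondary endpoint in section 8.4 falls under that last rule: "Humoral immunity: Magnitude of MERS-S-specific antibody responses as assayed by ELISA". Section 9.4.10.3.4 gives the outpatient sampling days: "Blood sampling for humoral immunogenicity (only on day 7, 14, 35, 42, 56, 84". Table 1a of the study schedules also marks ELISA on days 0 and 28.

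Two further rules bear on who reaches the per protocol set. Section 9.4.1 makes the second injection follow a review of the subject's own safety data: "The second immunization for each subject will be done after the Local Safety Board reviewed individual safety data of the respective subject". Section 9.4.10.4 says that subjects who leave early "will be replaced if they discontinue early or withdraw up to day 35".

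**The concern.** Until the second injection, a subject who later stops and one who later continues have had the same exposure: one injection at their cohort's dose. Their antibody results at days 7, 14 and 28 answer the same question. The plan summarises one subject's results and not the other's, on the basis of something that happens afterwards, possibly as late as day 35.

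That later event need not be unrelated to the vaccine. Adverse events are a listed reason for withdrawal (section 9.3.3.1), and the second injection follows an individual safety review. Section 7.3 describes adverse events with MVA vaccines as dose-dependent, so exclusions could differ between the two dose levels whose responses the secondary objective evaluates.

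Replacement means that a cohort table can show 12 subjects when 13 or 14 were vaccinated. The plan provides a second-population check for safety, where the main set already holds everyone vaccinated. It provides none for immunogenicity, where the only set is a selected one.

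**Working it through.** **Does any other text supply the missing summary?** The relevant rules side by side:

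| Question | Protocol text | Consequence |
|---|---|---|
| Which set for ELISA? | 9.8.1.2: per protocol, with no other set | No summary in all vaccinated subjects |
| Who is in that set? | 9.8.1.2: two injections, no withdrawal up to day 28 + 7 = day 35 | One-dose subjects and two-dose subjects who leave by day 35 are out |
| Are there samples before dose 2? | Table 1a and 9.4.10.3.4: days 0, 7, 14, 28 | Up to three post-baseline samples per excluded subject |
| Where do replaced subjects' data go? | 9.3.3.2: safety population; per protocol is named only for withdrawals after day 35 | Agrees with 9.8.1.2 |
| Are the values kept? | 9.8.1.3: individual values are listed | Omitted from summaries, not lost |

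I take the day 28 ELISA sample as drawn before the second injection. The before-immunization footnote stands on other day 28 rows of Table 1a but not on the ELISA row.

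**The plan's own figure.** The only number to reproduce is the sample size: 2 cohorts × 12 = 24, which agrees with section 9.8.2. There is no power calculation and no drop-out rate, so everything below is illustrative.

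**How likely is any exclusion?** Assume that each of 24 subjects independently leaves the per protocol set with probability q. Then P(at least one) = 1 − (1 − q)^24.

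| Assumed q | P(at least one of 24) |
|---|---|
| 2% | 38% |
| 5% | 71% |
| 10% | 92% |
| 20% | 99.5% |

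**How far could a response proportion move?** Assume that replacement keeps 12 in the per protocol set, that k further vaccinated subjects are excluded, and that each has a sample at the time point. With r responders among the 12, the proportion in all vaccinated lies between r/(12 + k), if no excluded subject responded, and (r + k)/(12 + k), if all did. For r = 9, the per protocol figure is 9/12 = 75%:

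| k | Lower | Upper |
|---|---|---|
| 1 | 9/13 = 69% | 10/13 = 77% |
| 2 | 9/14 = 64% | 11/14 = 79% |
| 3 | 9/15 = 60% | 12/15 = 80% |

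**How far could the magnitude move?** This is closer to the stated endpoint. If the excluded subjects' mean log10 titre differs by d from that of the 12, the all-vaccinated mean shifts by d·k/(12 + k). With excluded titres lower by d, the per protocol geometric mean divided by the all-vaccinated one is 10^(d·k/(12 + k)). For d = 0.5:

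- k = 1: 10^(0.5/13) = 1.09
- k = 2: 10^(1.0/14) = 1.18
- k = 3: 10^(1.5/15) = 1.26

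If the excluded subjects' titres are higher by the same amount, the ratios are the reciprocals: 1/1.09 = 0.92, 1/1.18 = 0.85 and 1/1.26 = 0.79. With k = 0 the ratio is 1.

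**The case against.** The strongest reply is that the regimen is two injections (sections 8.1 and 9.1), no single-dose response is named as an endpoint, and summarising those who received the regimen is defensible in a descriptive phase I trial. That stands for time points after dose 2. It is weaker at days 7 to 28, which the protocol chose to sample and where nobody has yet had the second injection.

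Several stronger readings are tempting but not supported:

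- **That the data are thrown away.** They are not. Section 9.8.1.3 lists individual values, and section 9.3.3.2 asks for withdrawn subjects' observations to be reported as fully as possible.
- **That the analysed set is selected on tolerating the vaccine.** Selection is on completing dose 2 plus 7 days. Section 9.3.3.1 also lists personal reasons, non-compliance, protocol violation and loss to follow-up, and nothing shows that intolerance would dominate or would track with titre.
- **That replacement conceals the exclusions.** Replacements carry the drop-out's number plus 100 (sections 9.3.3.1 and 9.4.10.2), and withdrawal reasons go into the eCRF. The information exists; the summary tables simply need not show it.
- **That the per protocol result must be too favourable.** The direction is unknown, and excluded subjects could be stronger responders.

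Two limits on size also stand. A subject who leaves before day 28 may have no day 28 sample and so would not enter that denominator. And dose escalation rests on safety data, with immunological data only as available (section 9.10), so no decision threshold depends on this summary.

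The separate analysis plan is not shown and could add a supportive table, but the protocol's restriction to one population, as worded, rules that out.

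**Conclusion.** The point holds in a limited form. Section 9.8.1.2 leaves antibody results at days 7, 14 and 28 out of the summary tables for vaccinated subjects who do not complete dose 2 plus 7 days, and no other section supplies that summary.

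The size is modest and of unknown sign. With one to three exclusions in a cohort, a 75% per protocol response could stand for anything from 60% to 80% among all vaccinated, and a 0.5 log10 difference in titre would move the geometric mean ratio to between 0.79 and 1.26. These figures assume that each excluded subject has a sample at the time point, and the exclusion counts and titre difference are mine, not the protocol's. For scale, the exact 95% interval around 9/12 is 43% to 95%, so sampling error at this size is larger than the shift. If nobody leaves by day 35, there is no effect.

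Severity is low: the endpoint is secondary, the trial is descriptive and no hypothesis is tested in a confirmatory sense. The change is still worth making, because each subject is 1/12, or about 8 percentage points, of a cohort.

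**What to change.** In section 9.8.1.2, replace the sentence that confines all non-safety endpoints to one population with text to this effect:

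> ELISA results up to day 28 (sample taken before the second injection) will be summarised by dose level in all vaccinated subjects with a baseline and at least one post-baseline sample; the per protocol population will be supportive at these time points. Results after the second injection will be summarised in the per protocol population.

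Beside the immunogenicity tables, show for each cohort the number vaccinated, the number excluded from the per protocol set and the number replaced, with reasons.

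The wider set should stop at day 28. Using it at later time points would mix any one-dose subjects still in follow-up with two-dose subjects and blur the response to the regimen.

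Cost: one additional set of descriptive tables on data already collected, with no new samples, visits or subjects. This is a cheap improvement, not a condition for the trial to be interpretable.

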9.8.1.3 Statistical analyses

For metric variables, the arithmetic mean (Mean), the standard deviation (SD), coefficient of variation (CV), absolute minimum (Min) and maximum (Max) and median (Med) will be reported per dose level. For parameters that appear to be log-normally distributed, the geometric mean (GeoM) and the coefficient of variation (CV) may be reported.

Laboratory values and their change from baseline will be summarized and displayed graphically by dose level. Values outside of the reference range will be flagged and tabulated. Unless otherwise specified, baseline is defined as the time-point closest to but prior to the first administration of the vaccine.

Categorical variables will be summarized by dose level in frequency tables (number and percentages).

The individual subject values will be listed.

It is not planned to test any hypotheses in a confirmatory sense. If deemed necessary, 95% confidence intervals will be provided for means (metric variables) and percentages (categorical variables).

Interim analyses may be performed upon request of the sponsor.

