
Test product, dose and mode of administration, batch number:
	
Test product: MVA-MERS-S
 
Dose:
 
 • In Cohort 1, 12 fasted subjects will receive 2 single doses of 1 x 10⁷ pfu₅₀ MVA-MERS-S in 0.5mL (total injected volume 1mL). • In Cohort 2, 12 fasted subjects will receive 2 single doses of 1 x 10⁸ pfu₅₀ MVA-MERS-S in 0.5mL (total injected volume 1mL). • In addition, irrespective of cohort, eligible subjects that consent to participate in and are eligible for a 3rd boost vaccination will receive

	
a 3rd single dose of 1×10^8 pfu MVA-MERS-S in 0.5mL (the total injected volume will then be 1.5mL).
 
The relative concentration of the test product is 2×10^7 pfu₅₀ /ml and 2×10^8 pfu₅₀ /ml, respectively.
 
Dose administration on day 0 and day 28 for each subject. Dose escalation will occur following a review of the interim safety report.
 
For eligible subjects, the 3rd vaccination will be administered 12 months after 1st vaccination \pm 4 months.
 
Mode of administration: Intramuscular (i.m.)

Duration of Treatment:	
Subjects will receive two single vaccine injections, one on day 0 and another on day 28.
 
In addition, eligible subjects will receive a boost vaccination 12 months (\pm 4 months) after the 1st vaccination.

Reference therapy, dose and mode of administration, batch number:	None
Criteria for evaluation:	
Primary Endpoints:
 
The nature frequency and severity of adverse events associated with MVA-MERS-S vaccine will be collected and measured as followed:
 
 • Occurrence of solicited local reactogenicity signs and symptoms for 14 days after vaccination. • Occurrence of solicited systemic reactogenicity signs and symptoms for 14 days after vaccination • Occurrence of unsolicited adverse events (AE) for 28 days after vaccination • Change from baseline of safety laboratory measures • Occurrence of serious adverse events (SAE) throughout the study period 
Secondary Endpoints:
 
Immunogenicity
 
 • Humoral immunity: Magnitude of MVA-MERS-S antibody responses
Safety:	
Safety data (AEs, SAEs and Vital Signs) will be collected at all study visits.
 
Laboratory safety test (biochemistry, hematology and dipstick urinalysis) will be performed at screening, pre-dose and at study follow-up visit.

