Statistical methods:	
Metric data will be summarized using descriptive statistics (number, mean, standard deviation, minimum, median and maximum). Categorical data will be summarized by using frequency tables (frequency and percent). It is not planned to test any hypotheses in a confirmatory sense.

STUDY SCHEDULES

Table 1a

Phase of study	SCR	Confinement			Ambulatory Visits			Confinement			Ambulatory Visits				End of study
Study day	-28- -2	-1	0	1	3	7	14 (±2)	27	28	29	35	42 (±2)	56 (±3)	84 (±3)	180 (±7)
Informed Consent	√														
I/E Criteria	√	√						√							
Medical History/ De-mographics	√														
Update Medical History		√						√							
Physical Examination	√	√ ^a						√ ^a				√ ^a			√
Height and Weight	√														√ ^c
Vital Signs	√	√	√ ^d	√	√	√	√	√	√ ^d	√	√	√	√	√	√
12-lead ECG	√					√	√		√		√	√			
Ambulatory Visit	√				√	√	√				√	√	√	√	√
Confinement		√	√	√ ^e				√	√	√ ^e					
Dosing			√ ⁱ						√ ⁱ						
Injection site & systemic events/ reactions assessment			√ ^d	√	√	√	√		√ ^d	√	√	√			√
Temperature	√		√ ^d	√	√	√	√		√ ^d	√	√	√	√	√	√
Alcohol Breath Test	√	√						√							
Discharge				√						√					
Training/ Dispensing subject diary			√						√						
Review/ Collection of subject diary				√	√	√	√	√		√	√	√	√	√	√
Adverse Events & Concomitant medication			√ ^d	√	√	√	√	√	√ ^d	√	√	√	√	√	√
Laboratory Analysis															
Phase of study	SCR	Confinement			Ambulatory Visits			Confinement			Ambulatory Visits				End of Study
Study day	-28- -2	-1	0	1	3	7	14 (±2)	27	28	29	35	42 (±2)	56 (±3)	84 (±3)	180 (±7)
Troponin T	√					√	√		√		√	√			√
Safety Lab blood (Clinical Chemistry, Hematology)	√	√		√	√	√	√	√		√	√	√			√
Safety Lab Urine	√	√				√	√	√			√	√			√
HIV/HBV/HCV Serology	√														
Urine Drug Screen	√	√						√							
Pregnancy Test	√ ^h	√ ^g						√ ^g							√ ^h
Anti-MVA-MERS Elisa			√			√	√		√		√	√	√	√	√
Neutralization Assay			√			√	√		√		√	√	√	√	√
T-cell response			√			√	√		√ ^f		√	√	√	√	√
RNA blood sample storage			√	√	√	√			√ ^f	√	√				

Innate immunity			√	√	√	√			√	√	√				
PBMC freezing and plasma aliquots			√	√	√	√	√		√ _f	√	√	√	√	√	√

Table 2b**3rd boost vaccination 8-16 months after initial vaccination**

Phase of study	Phone Call	Dosing	Ambulatory Visits				End of study
Study day	≥ - 7	0	1	3	7	14 (±2)	28(±2)
Informed Consent		√ _f					
I/E Criteria		√ _f					
Update Medical History		√ _f					
Physical Examination		√ _{af}					
Weight		√ _{fc}					
Vital Signs		√ _d	√	√	√	√	√
12-lead ECG		√ _f					

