8.2 Primary Endpoints

The safety, tolerability, and reactogenicity of the experimental vaccine MVA-MERS-S will be measured as followed:

- Occurrence of solicited local reactogenicity signs and symptoms for 14 days following the vaccination (see Table 3)
- Occurrence of solicited systemic reactogenicity signs and symptoms for 14 days following the vaccination (see Table 4 and Table 5)
- Occurrence of unsolicited AEs for 28 days following the vaccination
- Change from baseline of safety laboratory measures
- Occurrence of SAEs throughout the study period

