9.5.3.5.1 Adverse Events

The adverse events will be listed per subject using MedDRA terminology (preferred term and system organ class) and will be reported in tables summarizing the frequency of subjects with adverse events and adverse events by dosage level, by dose level and injection and by body system, the number of adverse events and number of subjects with adverse events by dosage level, by dosage level and injection, and the characteristics of adverse events.

For the hematology, clinical laboratory and the urine analysis deviations from the reference ranges will be summarized in frequency tables.

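### Section 9.8 was not adapted to the optional third vaccination: by default, post-boost laboratory change would be measured from a value 8–16 months old, and the dose grouping and boost denominator are left unclear

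*Protocol*

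**What the plan says.** **Baseline.** Section 9.8.1.3: unless otherwise specified, "baseline is defined as the time-point closest to but prior to the first administration of the vaccine". No other baseline is given in section 9.8. The primary endpoints in section 8.2 include "Change from baseline of safety laboratory measures".

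**Boost.** The Study Schedules head the extension "3rd boost vaccination 8-16 months after initial vaccination". The Synopsis and section 9.4.1 give it at 10^8 pfu in both cohorts, only to subjects who consent, with at most 12 per cohort. Safety laboratory blood is scheduled on boost days 0, 1, 3, 7, 14 and 28.

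**Grouping.** Section 9.8.1.3 summarises metric and categorical variables by dose level. Section 9.5.3.5.1 tabulates adverse events "by dosage level, by dose level and injection and by body system".

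**Analysis sets.** Section 9.8.1.2: "All subjects receiving at least once the study medication will be included into the safety evaluation". All safety endpoints are analysed in that set. The per protocol set is defined by two injections and by withdrawal after the second. Neither definition mentions a third injection.

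**The concern.** The design now allows three injections, but the statistical section still describes two. This is more than detail left to the SAP: the protocol states a default baseline and a single safety set, and neither fits the extension.

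At stake is how the boost safety results read. A laboratory shift over a year, from season, intercurrent illness or assay change, would enter the post-boost change from baseline and could be taken for a boost effect, or could hide one. A reader of a table headed by dose level could not tell whether cohort 1's boost sits under 10^7 or 10^8. If boost percentages were taken over everyone ever dosed, they would be too low whenever some subjects were not boosted. In a first-in-human safety trial that error favours the vaccine.

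**Working it through.** **1. Age of the baseline.** The Synopsis gives 12 ± 4 months: 12 − 4 = 8 and 12 + 4 = 16, which reproduces the window in the Study Schedules. The last boost visit is at day 28 ± 2, so at 26 to 30 days. At 30.44 days per month, 8 + 26/30.44 = 8.9 months and 16 + 30/30.44 = 17.0 months. With the boost day 0 sample, the baseline would be of the same day as the injection. The document gives no figure for laboratory drift, so the size of the distortion cannot be stated, only the age of the reference value.

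**2. Is the boost-day sample taken before dosing?** For doses 1 and 2, safety blood is scheduled on days −1 and 27, necessarily before injection. For the boost it is on day 0. The boost schedule (headed Table 2b) carries the footnote for sampling before immunization on the ECG, alcohol and pregnancy tests, but not on the safety laboratory or troponin rows. Section 9.4.10.3.5 lists both ahead of dosing and no blood draw after it, so sampling before dosing appears intended.

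**3. Meaning of 'dose level' at injection 3.** There are two readings. The counts are maxima and assume that all 12 + 12 subjects are boosted.
- *Dose injected.* The 10^8 results at injection 3 hold 12 + 12 = 24 subjects, half primed at 10^7 and half at 10^8. Over the whole trial, 10^8 injections number 12 × 3 + 12 = 48, of which 12 (12/48 = 25%) come from cohort 1.
- *Cohort.* This is the usage of section 9.8.2, with 12 subjects per dose level. Cohorts stay apart, but cohort 1's boost appears under 10^7: 12 of its 12 × 3 = 36 injections (33%) were given at 10^8.

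**4. Denominator.** If the safety population is used for injection 3, the reported rate is x/12 in place of x/b, where b is the number boosted in the cohort. The ratio is b/12. The document does not give b, so it is varied below, with an assumed event rate of one third among the boosted. With zero events the exact two-sided 95% upper limit is 1 − 0.025^(1/n).

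| Boosted of 12 (assumed) | Subjects with event | Rate on boosted | Rate on 12 | Zero-event upper limit, boosted | Zero-event upper limit, 12 |
|---|---|---|---|---|---|
| 3 | 1 | 33.3% | 8.3% | 70.8% | 26.5% |
| 6 | 2 | 33.3% | 16.7% | 45.9% | 26.5% |
| 9 | 3 | 33.3% | 25.0% | 33.6% | 26.5% |
| 12 | 4 | 33.3% | 33.3% | 26.5% | 26.5% |

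Twelve per cohort assumes no replacements. Section 9.3.3.2 keeps replaced subjects in the safety population, so the denominator could be larger.

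**The case against.** The strongest reply is that the protocol leaves room for all of this. The baseline rule yields to any other specification, and section 9.8.1 sends details to a SAP that was not available for this review. Section 9.8.1.3 reports values as well as changes, displays them graphically, flags those out of range and lists individual data, so the boost day 0 level would be visible. This stands in part: the information is not lost, and the SAP may already settle the matter. It does not remove the point that the stated default gives an unsuitable reference for a primary endpoint.

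Four stronger readings are tempting, and the document does not support them.
- *The plan pools the cohorts.* Section 9.8.2 uses dose level to mean cohort. On that usage the by-injection adverse event tables of section 9.5.3.5.1 already keep the cohorts apart. What remains is an ambiguous label.
- *Boost rates are divided by unboosted subjects.* Section 9.8.1.2 defines set membership, and no denominator for injection 3 is stated. The by-injection tables may well use recipients. The understatement is conditional.
- *Antibody rises are inflated by the old baseline.* The secondary endpoint in section 8.4 is the magnitude of the ELISA response; section 9.8.1.3 names change from baseline for laboratory values only.
- *A comparison of dose 3 with dose 2 is biased by self-selection.* No such comparison is planned.

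The missing footnotes on the boost schedule are weak evidence by themselves, given the order of procedures in section 9.4.10.3.5.

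**Conclusion.** The baseline point holds on the text as it stands. Unless something else is specified elsewhere, post-boost laboratory change would refer to a value 8–16 months old at the boost, and up to about 17 months old at its last visit, while a boost day 0 sample goes unused as baseline.

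The other two points hold as ambiguities. 'Dose level' does not describe injection 3 well on either reading. The only safety set defined would understate boost rates by the factor b/12 per cohort if used as the denominator: 0.25 to 0.75 for 3 to 9 boosted, and no effect if all 12 are boosted. The number boosted and the one-third event rate are assumptions.

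This is a worthwhile correction to descriptive summaries, not a threat to the trial's validity. No confirmatory test is planned, individual values are listed, and tables confined to injections 1 and 2 are unaffected.

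**What to change.** Amend section 9.8, or confirm that the SAP already does the following:

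- **Baseline.** For changes after the boost, use the last value before the third injection (boost day 0, pre-dose). Keep the value before the first dose as a supplementary baseline. Mark the boost-day safety laboratory and troponin draws in the boost schedule as taken before immunization.
- **Grouping.** Present boost results by original cohort and injection number, with the injected dose shown as a label.
- **Denominator.** Define a boosted safety set, all subjects who received the third injection, and use it for all post-boost summaries.

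The cost is wording, one schedule footnote and a few table shells. No new data are needed.
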